COMIRB Protocol

COLORADO MULTIPLE INSTITUTIONAL REVIEW BOARD [name] [contact] [contact]

Protocol #:15-0541Project Title:Effect of Urinary Alkalinization on Urine Uric Acid Precipitation and
Crystallization in Adults with Type 1 Diabetes

Principal Investigator: [name]. Version Date: 6/24/16

I. Hypotheses and Specific Aims: A brief statement of the purpose of the research project. This section should include the hypotheses and specific aims being tested in the research. *Note: If you are applying for QA/QI/PE determination, you should not use terms like "hypothesis" or "research;" Instead, use the terms "aims" or "goals" and "evaluation."*(Approx. 1 paragraph)

| Specific Aim 1: | To evaluate the ability of 2 doses of oral sodium bicarbonate (1950mg each) to alkalize urine over 24 hours in adults with type 1 diabetes and without chronic kidney disease. |
|------------------------|--|
| Hypothesis 1: | Sodium bicarbonate over 24 hours can increase urine pH by 0.5-1.0 in adults with type 1 diabetes and without chronic kidney disease. |
| Specific Aim 2: | To evaluate the effect of urinary alkalinization on urine uric acid concentration, precipitation and crystallization in adults with type 1 diabetes and without chronic kidney disease. |
| Hypothesis 2: | Increasing urine pH with oral sodium bicarbonate in adults with type 1 diabetes and without chronic kidney disease will solubilize urine uric acid thereby increasing urine uric acid, decreasing urine acid precipitation and crystallization |
| Specific Aim 3: | To evaluate the relationship between urine uric acid concentration, precipitation and crystallization with glomerular function and markers of tubular injury in adults with type 1 diabetes and without chronic kidney disease. |
| Hypothesis 3.1: | Urine uric acid concentration, precipitation and crystallization will be associated with markers of tubular injury (e.g. NGAL, MMP9) in adults with type 1 diabetes and without chronic kidney disease. |
| Hypothesis 3.2: | Urine uric acid concentration, precipitation and crystallization will be associated with estimated glomerular filtration rate (CKD-EPI creatinine and cystatin C) in adults with type 1 diabetes and without chronic kidney disease. |

In summary, this will be a pilot study with the aims to: 1) determine whether 2 doses of oral sodium bicarbonate (1950 mg per dose) over 24 hours can alkalinize urine in adults with type 1 diabetes and without chronic kidney disease; 2) determine the effect of urinary alkalinization on urine uric acid; and 3) examine the relationships between urine uric acid and glomerular function and markers of tubular injury.

The importance of this proposal relates to the major research and clinical need to understand the relationship between urine uric acid and diabetic tubular nephropathy in type 1 diabetes.

II. Background and Significance: Explain the background of this project so that we will understand why it is important to perform this research project. (Approx. 1 page)

Diabetic nephropathy is characterized not only by glomerular disease but also tubulointerstitial injury. The tubular changes associated with diabetic nephropathy, include basement membrane thickening, tubular hypertrophy, epithelial-mesenchymal transition, glycogen accumulation and interstitial inflammation (1). Although glomerular changes has received significantly more attention from researchers and clinicians than tubulointerstitial changes in diabetes, tubular injury is known to associate better with renal function than glomerular injury (2). In fact, tubular proteinuria may precede microalbuminuria with type 1 diabetes (3), suggesting that tubular damage may be induced earlier than glomerular injury in the course of diabetic nephropathy.

Serum uric acid (SUA) is lower in adolescents and adults with type 1 diabetes compared to non-diabetic peers (4, 5). Despite lower levels SUA remains an important risk factor for diabetic nephropathy in type 1 diabetes (6), with a large clinical trial underway examining the ability of allopurinol to prevent early renal loss (7). Several mechanisms have been proposed to explain the lower levels of SUA in type 1 diabetes including glucosuria induced uricosuria leading to spilling of urine uric acid (UUA) and lowering of SUA (8), and the notion that intracellular uric acid (IUA) and/ or UUA rather than SUA may be responsible for the development of complications. Animal studies have demonstrated that blocking uric acid production protects the kidney from tubulointerstitial injury, which suggests a causal role for uric acid in the development of diabetic tubular injury (9, 10). Relative dehydration, secondary to glucosuria, exercise or inadequate liquid intake, may lead to concentrated and acidic urine, which may cause UUA to precipitate and crystallize in type 1 diabetes (11-14). The UUA precipitation and crystallization is thought to induce inflammation and injury of the tubules with possible retrograde glomerular injury (11-14). Moreover, it was recently shown that UUA promoted apoptosis in human proximal tubular cells by oxidative stress and activation of NADPH Oxidase NOX 4 (15).

Oral alkali replacements are readily available, safe and include the following formulations sodium bicarbonate, BiCitra (sodium citrate and citric acid), PolyCitra (citric acid, sodium citrate, and potassium citrate), polycitra-K (potassium citrate and citric acid). In contrast to sodium bicarbonate, citrate is converted to bicarbonate in the liver and thus this conversion is affected by liver disease. Usual adult doses for urinary alkalinization are 325 to 2000 mg orally 1 to 4 times a day. One gram provides 12 mEq (mmoL) each of sodium and bicarbonate, and is titrated to a goal of urine pH of 8.0. In a prospective open-label trial 4 g of sodium bicarbonate was administered orally 3 times daily to 9 healthy volunteers for 24 hours, and after 10 hours all participants had a urine pH \ge 7 and after 20 hours all participants had urine pH \ge 8. No adverse effects or abnormal blood results were documented during the 24-hour follow-up (16). Urinary alkalinization should solubilize UUA thereby increasing the concentration of uric acid in urine and decreasing precipitation and crystallization in type 1 diabetes.

With diabetic nephropathy being the leading cause of end-stage renal disease in the Western world. Novel therapeutic targets could help halt the progression of kidney disease in people with type 1 diabetes, thereby improving morbidity and mortality, and lessen the public health burden. While the currently available therapies focus on the glomerular injury of diabetic kidney disease, urine uric acid crystallization is associated with tubular injury, and is thought to precede the onset of glomerular disease in type 1 diabetes. Earlier interventions could decrease the rate of renal function loss and prolong the time to development of end stage renal disease. UUA is a particularly attractive therapeutic target due to the potential to reduce tubular injury with sodium bicarbonate. Furthermore, the ongoing Prevent Early Renal Loss (PERL) study with \$27 million in NIH funding will determine if lowering uric acid with allopurinol slows decline in renal function, and sodium bicarbonate to alkalize urine could be a complementary, safe and cheap treatment. Accordingly, we propose a pilot experimental study examining the effect of urine alkalinization with oral sodium bicarbonate on UUA precipitation and crystallization in adults with type 1 diabetes.

III. Preliminary Studies/Progress Report:

Unpublished data in adolescent with type 1 diabetes demonstrated a positive relationship between urine pH and urine uric acid (r=0.48, p<0.0001, n=99, **Figure 1**), suggesting increased solubility of urine uric acid with more alkaline urine.

Preliminary data from adolescents with type 1 diabetes in the *Determinants of Macrovascular Disease* cohort.

However, no data exist on whether urinary alkalinization by sodium bicarbonate can increase solubility of urine uric acid and reduce precipitation and crystallization thereby preventing tubular injury.

IV. Research Methods

A. Outcome Measure(s):

Urine uric acid concentration, precipitation and crystallization measured before and after sodium bicarbonate treatment to increase urine pH.

B. Description of Population to be Enrolled:

Inclusion criteria: In this study we will aim to recruit 78 adults, both males and females aged 18-60 years with type 1 diabetes. Assuming 80% of subjects approached will be eligible to participate and 60% of eligible subjects will consent to participate, this provides at least 47 subjects which is needed for power of 0.8 to detect effect size of 20% in change in urine uric acid.

- Participants must be able to be fasting prior to study visit #2 and #3 at CTRC
- Participants must be able to give informed consent.

Visit #1 will take place at Barbara Davis Center in association with the participants' regular diabetes visit. We plan to meet them before or after their regular visit to discuss study

details including the pre-study diet, review medical history to determine study eligibility and consent eligible and interested participants. This visit will determine eligible prior to diet, urine and blood collection and thereby minimize risk and participant burden. We will also obtain consent from eligible participants during this visit.

Exclusion Criteria:

- Non-type 1 diabetes
- History of eGFR <60 ml/min/1.73m² or albuminuria
- History of hypocalcemia or at risk of hypocalcemia (metabolic alkalosis increases binding of calcium to albumin causing a low ionized calcium which can in rare cases cause laryngospasms, paresthesia and seizures in those with already low calcium)
- Taking allopurinol or uric acid altering medications
- Ketogenic diet (secretory mechanisms for uric acid may be inhibited by lactate, betahydroxubutyrate and acetoacetate)
- Ketonuria (secretory mechanisms for uric acid may be inhibited by lactate, betahydroxubutyrate and acetoacetate)
- Taking phosphorus binders (e.g. sevelamer)
- Taking blood pressure medications
- Taking SGLT2 inhibitors
- Pregnant or breastfeeding
- Taking the following medications which may interact with sodium bicarbonate (phentermine, pseudoephedrine, antifungal medication, cephalosporin antibiotics [e.g. Keflex], tetracycline antibiotics [e.g. doxycycline], steroids or lithium)

C. Study Design and Research Methods

Participants will be recruited from Diabetes Clinic at Barbara Davis Center. Informed consent will be obtained following standard COMIRB approved methods by the PI and/or members of the research team.

Sodium Bicarbonate Dose

- 3900mg (2x doses 1950 mg) of Sodium Bicarbonate over 24 hours was decided on based on the following:
 - Usual adult daily doses for Sodium Bicarbonate are 1,200-8,000mg with 1 gram providing 12 mEq (mmoL) each of sodium and bicarbonate.
 - For urinary alkalinization (with a goal urine pH of 8.0) doses tend to be greater and up to 12,000 mg daily (16).
 - We do not aim to alkalinize the urine of our participants (urine pH > 8.0) but rather normalize the relatively acidic urine found in participants with type 1 diabetes, by increasing the urine pH by 0.5 – 1.0.
 - Extrapolating from published urinary alkalinization data (16) and discussing with [name] we decided on approximately 4,000mg divided BID over 24 hours. Sodium Bicarbonate comes in 650mg tablet dosing which led to 1,950mg BID (3,900mg).

Recruitment

Participants will be recruited from Adult Diabetes Clinic at Barbara Davis Center by phone. We will discuss study details including the pre-study diet and fasting instructions. Interested participants will be mailed:

- Fasting instructions (for visit #1 and visit #2)– Patients will be asked to fast after midnight and will be asked to omit caffeine and smoking prior to the visit and
 - Fasting and insulin dosing instructions will be provided for the participants to reduce risk of hypoglycemia (these instructions are similar to what is provided once patients with type 1 diabetes come in for fasting labs)

- Participants will fast for only 8 hours
- Participants on insulin pump will be informed to not give themselves a bolus in the morning since they are fasting
- Participants on taking insulin by injections will be informed to not give themselves a bolus in the morning since they are fasting
- Diet instructions (for visit #1 and visit #1) Patients will be asked to maintain a moderate protein (1.5g/kg of weight), and high sodium diet (3,450 mg of sodium per day) for one week prior to the study visit #1, and between study visit #1 and #2.
- Copy of patient information and consent form to review

Study Visit #1

Visit #1 will take place at Adult CTRC or Barbara Davis Center. Medical history will be reviewed and eligibility determined. . Informed consent will be obtained from eligible participants following standard COMIRB approved methods by the PI and/or members of the research team.

At this visit, participants will present fasting from midnight, height, weight and blood pressure will be measured. Urine will be collected and blood will be obtained via venipuncture by RN or venipuncture-trained PRA. The baseline blood will be drawn for serum uric acid, serum glucose, serum creatinine and serum cystatin C. Urine will be collected for urine pH, urine ketones, urine glucose, urine creatinine and urine uric acid. The urine will also be examined for precipitation and crystallization of urine uric acid. The participant will take 1950mg of sodium bicarbonate (3 x 650mg tablets) with water. We estimate that the study visit will take 60 minutes. After completion of the study visit, the participant will receive the second dose of sodium bicarbonate to take approximately 12 hours after the first dose (1950mg of sodium bicarbonate [3 x 650mg tablets]).

The participants will need to remain on the moderate protein and high sodium diet until completion of study visit #2. We will have provide protein bars, or participants may bring their own high protein snack.

Study Visit #2:

Visit #2 will take place at Adult CTRC or Barbara Davis Center. Participants will present fasting from midnight. Urine will be collected and blood will be obtained via venipuncture by RN or venipuncture-trained PRA. Blood will be drawn for serum uric acid, serum glucose, serum creatinine and serum cystatin C. Urine will be collected for urine pH, urine ketones, urine glucose, urine creatinine and urine uric acid. The urine will also be examined for precipitation and crystallization of urine uric acid.

D. Description, Risks and Justification of Procedures and Data Collection Tools:

Labs methods: Serum creatinine, serum cystatin C, serum uric acid and serum glucose will be determined using standard methods in the CTRC core lab and [name]'s lab. Urine uric acid, urine glucose, urine creatinine and urine pH will be measured at [name]'s lab. Urine ketones will be checked at BDC.

Sample banking: Residual blood and urine volume will be stored for future research, in particular to use when new and promising urinary and serum biomarkers become available.

Sodium bicarbonate: Three tablets of 650mg of sodium bicarbonate (1950mg) will be given twice a day to all participants. [name] Pharm.D. will arrange and dispense medications. Prescriptions will be written for the dose to be taken by the participants at home.

Other forms: Standard medical history will be obtained (see accompanying forms in submission packet).

Estimation of GFR: Various equations have been developed to estimate GFR based on either serum creatinine or cystatin C plus other variables. We will employ the state of the art CKD-EPI combined creatinine and cystatin C to calculate estimated GFR in our participants.

CKD-EPI combined creatinine and cystatin C eGFR = eGFR = 135 x min(serum creatinine/k, 1)^{-a} x max(serum creatinine/k, 1)^{-0.601} x min(serum cystatin C/0.8, 1)^{-0.375} x max(serum cystatin C/0.8, 1)^{-0.711} x 0.995^{age} [x 0.969 if female] [x 1.08 if black]

Compliance:

To improve compliance, the first dose of sodium bicarbonate (1950 mg) will be administered at the visit #2 at CTRC. Moreover, participants will be asked to set an alarm on their phone for the second and final dose (1950mg) at home.

Plan to minimize risk:

1. Fasting and hypoglycemia:

Fasting will be limited to 8 hours, and detailed fasting and insulin instructions will be given to participants.

2. Venipuncture to draw blood for lab tests:

Venipuncture will be performed by research personnel with experience with venipuncture to reduce risk of pain. Gloves will be worn and the area of skin cleaned to prevent risk of infection.

3. Sodium bicarbonate administration:

The study participant will be monitored for a minimum of an hour after the administration of the first sodium bicarbonate dose to check for any reaction. The study participant will be told to call with any issues or concerns at home. Participants taking medications known to interact with sodium bicarbonate will be excluded from participating.

E. Potential Scientific Problems:

In any clinical study unforeseen human factors provide challenges. The current study is based upon a previous study with sodium bicarbonate administration in adults with no reported adverse effects. Furthermore, we aim to use lower doses of sodium bicarbonate in this study. We have also performed careful power analyses to allow meaningful analyses.

F. Data Analysis Plan:

(A HIPAA compliant, Red Cap database system will be used for this study.)

| Outcome | Effect size | SD pre and post | Correlation of pre with post | SD of change | Power | Ν |
|--------------------|-------------|--------------------|------------------------------------|-----------------|-------|----|
| Urine pH | 0.5* | 0.42 | 0.5 | 0.42 | >99 | 20 |
| | 1.0* | 0.42 | 0.5 | 0.42 | >99 | 10 |
| Urine uric acid | 10% | 16.48 | 0.95 | 5.21 | 80 | 47 |
| | 20% | 16.48 | 0.80 | 10.42 | 80 | 47 |

Table 1 Power calculations:

* Units on the pH scale

Per our power analysis, with a sample size of 50 we will have power of 0.8 to detect effect size of 20% change in urine uric acid following 24-hours of NaHCO₃. Paired t-test will be employed to evaluate whether the change in urine uric acid pre- and post NaHCO3 administration is statistically significant. We will also adjust for covariates with ANCOVA or linear regression models [ANCOVA vs. linear regression models will be decided based on the variation of urine uric acid at baseline in our participants].

We will also calculate fractionated excretion of uric acid (FeUA = [(UUA * SCr / SUA * UCr)*100]), and regress FeUA, SUA and UUA on eGFR calculated by CKD-EPI creatinine and cystatin C. Furthermore, we will also regress blood glucose and urine glucose on FeUA, SUA and UUA.

G. Summarize Knowledge to be Gained:

Diabetic nephropathy remains the leading cause of end-stage renal disease and dialysis in the US. While diabetic glomerulopathy has received significant attention from researchers and clinicians, determinants of tubulointerstitial injury in diabetes are less well examined. Compared to glomerular injury, tubular injury is known to associate better with renal function in diabetes (2). In fact, tubular proteinuria may precede microalbuminuria with type 1 diabetes (3), suggesting that tubular damage may be induced earlier than glomerular injury in the course of diabetic nephropathy. Animal studies have demonstrated that blocking uric acid production protects the kidney from tubulointerstitial injury, which suggests a causal role for uric acid in the development of diabetic tubular injury (9, 10). Acidification of urine is associated with urine uric acid crystallization which may lead to tubular injury (11, 12). For that reason, urine alkalinization with sodium bicarbonate is a safe and potentially effective therapy to increase solubility of urine uric acid and prevent crystallization and associated tubular injury. Urine alkalinization could potentially prevent or halt progression of diabetic nephropathy in type 1 diabetes.

H. References:

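### At the stated 80% eligibility and 60% consent, 78 adults give about 37 participants, not 47; if recruitment stopped at 78 approached, power would be about 70%

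*Combined protocol and SAP*

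**What the plan says.** Section IV.B (Description of Population to be Enrolled) states the recruitment aim, "In this study we will aim to recruit 78 adults", and continues: "Assuming 80% of subjects approached will be eligible to participate and 60% of eligible subjects will consent to participate, this provides at least 47 subjects". It calls 47 the number needed for 0.8 power to detect a 20% change in urine uric acid. The 80% is a fraction of those approached and the 60% a fraction of those eligible.

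In section IV.F (Data Analysis Plan), Table 1 has the matching row for urine uric acid, "20% | 16.48 | 0.80 | 10.42 | 80 | 47": effect, SD before and after, correlation, SD of change, power and N. The paragraph under the table gives a different N for the same power and effect: "with a sample size of 50 we will have power of 0.8 to detect effect size of 20% change in urine uric acid". The planned test is a paired t-test. Neither section states the significance level, the sidedness or the baseline mean of urine uric acid.

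**The concern.** The sentence in IV.B starts from 78 and applies two successive rates. Their product is 0.48, so fewer than half of those approached would be enrolled. Forty-seven is 60% of 78, so the 80% seems to play no part in the result.

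This matters because 78 is the only recruitment number in the protocol. If the study team treats it as the number of adults to approach, expected enrolment falls below the N that the protocol says it needs for urine uric acid. Urine uric acid is a named outcome and, apart from urine pH, the only one with a power calculation. The 47 and 50 in IV.F leave the enrolment target itself unsettled.

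**Working it through.** **Inputs.** From IV.B: 78 adults, 80% eligible, 60% consenting, 47 needed. From IV.F, Table 1: SD 16.48, correlation 0.80, SD of change 10.42, 80% power at N = 47. From the text under Table 1: N = 50 for the same power. Assumed, because not stated: alpha 0.05, two-sided, with one-sided as a sensitivity check.

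**1. The plan's figure.** 78 × 0.60 = 46.8, which rounds to 47. The stated yield is reproduced with the consent rate alone.

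**2. Both stated rates.** 78 × 0.80 = 62.4 eligible; 62.4 × 0.60 = 37.44 enrolled. The shortfall is 47 − 37.44 = 9.56, or 9.56/47 = 20%.

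**3. Working back from the target.**
- For 47: 47/(0.80 × 0.60) = 97.9, so 98 approached. Check: 98 × 0.80 = 78.4 eligible; × 0.60 = 47.04 enrolled.
- For 50: 50/0.48 = 104.2, so 105 approached. Check: 105 × 0.80 = 84 eligible; × 0.60 = 50.4 enrolled.

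**4. Could chance close the gap?** Treat those approached as independent, each with probability 0.48 of enrolling. With 78 approached, the binomial probability of at least 47 enrolled is 0.020, and the 2.5% and 97.5% points are 29 and 46.

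**5. Table 1's SD of change.** SD × √(2(1 − r)) = 16.48 × √(2 × 0.20) = 10.42, as printed. Nothing here shows Table 1's N = 47 to be wrong.

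**6. Power at 37.** Without the baseline mean, the 20% change cannot be turned into an absolute difference directly. The standardised paired effect d (mean change divided by SD of change) was therefore solved from the plan's own statement of 80% power, anchored at N = 47 or at N = 50, using the noncentral t distribution with N − 1 degrees of freedom and noncentrality d√N. Power was then evaluated at other N. The change detectable with 80% power at N = 37 is 20% × d₃₇/d, where d₃₇ is the effect giving 80% power at 37: 0.473 two-sided, 0.417 one-sided.

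| Test | 80% power anchored at | d | Power, N = 37 | Power, N = 47 | Power, N = 50 | Detectable change, N = 37 |
|---|---|---|---|---|---|---|
| Two-sided | 47 | 0.417 | 69.5% | 80.0% | 82.5% | 22.7% |
| Two-sided | 50 | 0.404 | 66.7% | 77.4% | 80.0% | 23.4% |
| One-sided | 47 | 0.368 | 71.0% | 80.0% | 82.2% | 22.6% |
| One-sided | 50 | 0.357 | 68.6% | 77.8% | 80.0% | 23.4% |

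A simulation of the first row (200,000 runs) gave 69.6%, 80.1% and 82.6% at N = 37, 47 and 50.

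**7. Urine pH.** Table 1 needs 20 participants for a 0.5-unit change ("0.5* | 0.42 | 0.5 | 0.42 | >99 | 20") and 10 for a 1.0-unit change. An enrolment of 37 covers both.

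**The case against.** The best defence is that 78 was meant as the number of eligible adults. IV.B never calls 78 the number approached, and the chain of 98 approached, 78 eligible and 47 consenting fits every printed figure. On that reading 47 is correct, and the fault is an unlabelled 78 and a missing 98. This is plausible and may well be how the number arose. It does not rescue the sentence, because the 80% is tied to those approached, 78 is not labelled as eligible, and the number to approach is absent. The passage needs correcting on either reading.

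The power loss is also hypothetical. No section stops recruitment at 78. If enrolment continues to 47, power is untouched and only the recruitment forecast is wrong. This is accepted, and it is why the 70% is stated as conditional. That the study is a pilot does not change the point, since the protocol itself claims 0.8 power.

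The 47 against 50 discrepancy may be simple rounding up: if 47 gives 80%, 50 gives about 82%, which still meets a 0.8 target. That is fair, and the point is editorial. Still, a protocol should carry one target.

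Finally, 98 approached secures about 47 consents, not necessarily 47 complete pairs. Ketonuria is an exclusion, IV.C collects urine ketones at visit #1, and no dropout allowance is given. This stands as a caution on the corrected figure.

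**Conclusion.** The concern holds. As written, the yield in IV.B is wrong: both stated rates applied to 78 give 37, not 47, a shortfall of about 10 participants (20%). This part needs no assumption beyond the plan's own rates.

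The consequence for power is conditional on stopping at 78 approached. It would then be about 70% (66.7% to 71.0%) for a 20% change, with 80% power only for a change of about 23% (22.6% to 23.4%). Those figures assume alpha 0.05, the plan's own 80% power at 47 or 50, and a complete pair of measurements from everyone who consents.

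The correction should be made before the recruitment number is relied on. The error is certain, its effect on power depends on how 78 is used, and the remedy is cheap.

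A minor side note: the other urine uric acid row, "10% | 16.48 | 0.95 | 5.21 | 80 | 47", is internally consistent, but its 80% power depends on the correlation of 0.95. With the 0.80 used in the 20% row, power for a 10% change at N = 47 would be about 29% (27% to 34%). No reason is given for the two values.

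**What to change.** Choose one of two corrections in IV.B:

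- **Keep 47.** Define 78 as the number of eligible adults, and state either that about 98 must be approached or that recruitment continues until 47 are enrolled. Approaching 98 means about 20 more people than 78, with the enrolment target unchanged.
- **Keep 78 approached.** State an expected enrolment of about 37, with about 70% power for a 20% change and 80% power for a change of about 23%. The cost is a lower claimed power.

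Then use one N in IV.B, Table 1 and the text under the table. If the target is 50, about 105 adults must be approached (84 eligible), and the stated power becomes about 82% if Table 1's 47 is right. Say whether the target counts consents or complete pairs.

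It would also help to give the alpha, sidedness and baseline mean behind Table 1, and to note that the 10% row depends on the 0.95 correlation. All of this is a wording amendment; the design and the analysis do not change.

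### Low ionized calcium from alkalosis is named as a drug risk, but the plan measures neither calcium nor bicarbonate and describes no symptom check after the dose taken at home

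*Combined protocol and SAP*

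**What the plan says.** **The risk.** The Exclusion Criteria in IV.B explain that "metabolic alkalosis increases binding of calcium to albumin causing a low ionized calcium". The same bullet then qualifies the harm, describing this as a change "which can in rare cases cause laryngospasms, paresthesia and seizures in those with already low calcium". The exclusion itself reads "History of hypocalcemia or at risk of hypocalcemia". Being at risk is not defined. Under Study Visit #1 in IV.C, "Medical history will be reviewed and eligibility determined"; no calcium test is listed for that step.

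**The blood panels.** At Visit #1, "The baseline blood will be drawn for serum uric acid, serum glucose, serum creatinine and serum cystatin C". At Visit #2, "blood will be drawn for serum uric acid, serum glucose, serum creatinine and serum cystatin C". The Labs methods paragraph in IV.D names the same four serum analytes.

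**Observation.** Item 3 of the plan to minimize risk in IV.D states: "The study participant will be monitored for a minimum of an hour after the administration of the first sodium bicarbonate dose". Participants are also told to phone if anything worries them at home. Dose 2 is taken there, about 12 hours after dose 1. The Visit #2 text covers fasting attendance, blood and urine; it mentions no question about symptoms or adverse events. IV.A lists no safety outcome and IV.F no safety analysis.

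**The safety claim.** Section II cites an open-label study in 9 healthy volunteers who took 4 g three times daily for 24 hours, and reports: "No adverse effects or abnormal blood results were documented during the 24-hour follow-up". Section IV.G describes alkalinization with sodium bicarbonate as safe.

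**The concern.** The protocol identifies one specific biochemical route to harm and thinks it important enough to exclude people for it. Nothing that the study measures would show whether that route is active. An unrecognised low calcium at baseline would not be seen, and neither would a rise in bicarbonate or a fall in calcium on treatment. The ketonuria exclusion, by contrast, has a matching test: urine ketones are collected at both visits.

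Reporting of symptoms has a similar gap. After the participant leaves the dosing visit, the plan depends on the participant choosing to call. Paresthesia, the mildest of the three named consequences, could easily go unreported unless someone asks. A report of no adverse effects would then be hard to interpret, because no adverse effects reported spontaneously is not the same as none found on asking everyone. A pilot that proposes the treatment for wider use should be able to tell these apart.

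**Working it through.** **1. Reproduce the dose.** Inputs from IV.C: 650 mg tablets, three per dose, two doses.
- Per dose: 3 × 650 = 1,950 mg.
- Total: 2 × 1,950 = 3,900 mg. This matches the protocol.

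**2. Alkali load.** Section II gives 12 mEq of bicarbonate per gram.
- Per dose: 1.95 × 12 = 23.4 mEq.
- Total: 3.9 × 12 = 46.8 mEq.
- Cited study: 4 g × 3 = 12 g per day, and 12 × 12 = 144 mEq.
- Ratio: 46.8 / 144 = 32.5%, so the cited study gave about three times this daily load.

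**3. Named risk against planned measurement.**

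| Element of the stated risk | Measured at Visit #1 | Measured at Visit #2 | In the IV.D laboratory list |
|---|---|---|---|
| Metabolic alkalosis (serum bicarbonate) | No | No | No |
| Calcium, total or ionized | No | No | No |
| Albumin in serum | No | No | No |
| Symptoms | Observation after dose 1 | Nothing described | Not applicable |

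**4. Scheduled observation by dose.**
- Dose 1: at least 1 hour.
- Dose 2: none scheduled at the time. The guaranteed hour ends about 12 − 1 = 11 hours before it.
- Share of the load taken without scheduled observation: 23.4 / 46.8 = 50%.
- Visit #2 is a later in-person contact, but its listed content is sample collection only.

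**5. Two inconsistencies that bear on this.**
- *Time.* IV.C estimates about 60 minutes for the whole of Visit #1, which covers history, consent, measurements, sampling and then dose 1. IV.D requires at least 60 minutes after the dose. If the monitoring is part of the visit, 60 − 60 = 0 minutes remain for everything else.
- *Visit.* IV.C gives dose 1 at Visit #1; the Compliance paragraph in IV.D gives it at Visit #2. IV.B speaks of fasting before Visits #2 and #3, so the Compliance wording may follow a three-visit numbering in which a post-dose draw still exists. Read against the two visits in IV.C, however, it leaves unclear whether any listed draw follows dosing.

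**6. What a systematic question could show.** If all n participants are asked and none reports an event, the one-sided 95% upper bound on the event rate is 1 − 0.05^(1/n).
- n = 47 (IV.B and Table 1): 6.2%.
- n = 50 (text of IV.F): 5.8%.

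This is enough to describe common symptoms, not to exclude rare ones.

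**The case against.** The best defence is that the risk is small and already handled. The protocol calls the serious outcomes rare and ties them to people with already low calcium, and those known to be in that group are excluded. Other exclusions, for reduced eGFR, albuminuria, phosphorus binders and interacting drugs, narrow the population further. The total dose lies within the usual adult daily range given in IV.C and is about a third of a regimen after which no abnormal blood results were reported. The hour of monitoring is a minimum, participants can call, and Visit #2 brings them back. Safety is not among the three aims. All of this stands, and it is why the point is modest. The lower dose and the exclusion reduce the expected risk, but they do not produce data on it.

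Some of the absence also cannot be checked. The medical history forms are not in the available documents and the consent pages were removed, so either might contain relevant items. Residual blood is banked, but no calcium or bicarbonate assay on it is planned.

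A reader might infer three stronger things that the documents do not support:
- *That observation stops before the effect appears.* The 10-hour and 20-hour figures in Section II are urine pH. They are times by which every participant had reached a level, not times of onset, and they come from about three times this daily dose. The documents give no timing for serum alkalosis or ionized calcium.
- *That participants in general face seizures or laryngospasm.* The text limits this to rare cases in people with already low calcium.
- *That eligibility must rest on a measured calcium.* An exclusion based on history and a four-analyte panel do not contradict each other. Whether history alone is enough is a clinical decision for the sponsor.

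**Conclusion.** The point holds as a gap in safety data collection. A named biochemical risk has no corresponding measurement at either visit, half of the load (23.4 of 46.8 mEq) is taken with no scheduled observation, and no later symptom enquiry is described. The description of the treatment as safe will therefore gain no systematic support from this trial. The efficacy analyses are unaffected, and nothing here shows that participants would be harmed. It is a cheap improvement, worth making.

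The conclusion assumes that the visit descriptions and laboratory list are complete, and that the unseen forms contain no symptom script for use after dosing. If such a script exists, the gap narrows to the missing assays. The two inconsistencies over the dosing visit and the visit length need reconciling in any case, because they determine whether blood is drawn after dosing and whether the stated monitoring fits.

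**What to change.** In IV.C:
- At Study Visit #2, add a short scripted symptom and adverse-event question put to every participant, recording separately the time since dose 1 and since dose 2.
- At Visits #1 and #2, add serum calcium with albumin and serum bicarbonate to the blood already drawn, and add them to the laboratory list in IV.D.

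In IV.F, add a descriptive safety summary: the number asked, the number with any event by dose, with an exact 95% interval, and the paired change in calcium and bicarbonate with its spread and range. No hypothesis test is needed.

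The sponsor should also reconcile IV.C with the Compliance paragraph of IV.D on which visit gives dose 1, and the visit estimate of about 60 minutes with the monitoring requirement in IV.D. Any thresholds, and how abnormal results are handled, are for the sponsor to decide.

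The cost is a protocol amendment, a few minutes of questioning and a few routine assays per visit, with no extra visit or needle-stick. The Visit #2 results come after dosing has ended, so they describe safety and cannot protect that participant during treatment. Results from the baseline draw may likewise not be available before dose 1, which IV.C gives at the same visit.
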